8.5 DERIVED AND TRANSFORMED DATA

The time to event will be calculated for each of the following variables as detailed in

Table 8-2:

- Hospitalization due to a cardiopulmonary indication
- Exacerbation of underlying disease
- Death

Table 8-2 Derivation of Time to Event

Parameter	Scenario	Formula	Status
Time to hospitalization (weeks)	Subjects with hospitalization during the study	= (Hospitalization date – first visit date +1)/7	0 (event)
	Subjects without hospitalization during the study	= (Last assessment date – first visit date +1)/7	1 (censored)
Time to exacerbation (weeks)	Subjects with exacerbation during the study	= (Exacerbation date – first visit date +1)/7	0 (event)
	Subjects without exacerbation during the study	= (Last assessment date – first visit date +1)/7	1 (censored)
Time to death (weeks)	Subjects who died during the study	= (Death date – first visit date +1)/7	0 (event)
	Subjects who completed or discontinued prematurely	= (Last assessment date – first visit date +1)/7	1 (censored)

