12 breaths (6 to 72 mcg) four times daily to achieve daily doses of 24 to 288 mcg. The longest duration of inhaled treprostinil exposure in the open-label study was 5.4 years and the mean duration 2.3 years. There were observed improvements in median 6MWD at 6, 12, 18 and 24 months of 28, 31, 32 and 18 meters, respectively. These data support the durability of improvement in 6MWD obtained with inhaled treprostinil as demonstrated during the doubleblind phase of the study. Therapeutic benefit was also noted with improvements in the Borg dyspnea score, NYHA functional classification and quality of life (QOL). Survival was robust with one and two year Kaplan-Meier survival estimates of 97% and 91%, respectively, for subjects that remained in the trial. The most frequently reported AEs during the openlabel study were cough (39%), headache (31%), upper respiratory tract infection (22%), and nausea (22%). There were no clinically significant changes in clinical chemistry or hematology parameters. Unique findings that related to the inhaled route of administration, in addition to cough, were throat pain and throat irritation, occurring in 12% and 10% of subjects, respectively. These events were usually of mild or moderate severity and transient in duration. In a few subjects, these specific AEs were more pronounced as six subjects (3%) discontinued inhaled treprostinil due to cough, including one subject (<1%) with dry throat (Benza 2011).

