#### 10.3 ANALYSIS PLAN

All safety and efficacy data will be summarized in tables and listings and analyzed for trends over time. No formal hypothesis testing is planned.

The safety population will be defined as all subjects in the study that received inhaled treprostinil at any time during the course of the study. Safety analyses will be performed on the safety population. All AEs as recorded by the Investigators will be assigned MedDRA preferred terms by the sponsor for reporting purposes.

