11 SAFETY ANALYSES

11.1 ADVERSE EVENTS

AEs are captured from the time the Informed Consent Form is signed. Any AEs that are ongoing at the Study Termination Visit from study RIN-PH-201 are recorded as continuing AEs in the RIN-PH-202 study. All AEs with an onset date on or after the first dose of inhaled treprostinil in the RIN-PH-202 study or AEs ongoing from the parent study will be included in data listings and summaries.

The AEs will be coded using the Medical Dictionary for Regulatory Activities (MedDRA), and all summaries will utilize the Preferred Term (PT) and/or System Organ Class (SOC) to categorize AEs. All AEs will be organized by treatment group in the parent study and listed by subject, including onset date (day), cessation date (day), verbatim term, corresponding

SOC and PT, seriousness, date AE became serious, severity, frequency, relationship to study drug, action taken with study drug, and outcome.

The overall summary of AEs includes the number of subjects with any AE, the number of subjects with any study drug-related AEs, the number of subjects with AEs leading to study drug withdrawal, the number of subjects with AEs leading to death, the number of subjects with any serious AEs, and the number of subjects with any study drug-related serious AEs.

The summaries of AEs by SOC and PT will be provided by parent study treatment group and overall. The summaries of AEs, serious AEs, non-serious AEs, AEs probably or possibly related to inhaled treprostinil, and AEs leading to permanent discontinuation of inhaled treprostinil will include the number of subjects (percent of subjects) and number of events for each reported PT.

The total number of AEs and the AE rates will be calculated and summarized for each display, as appropriate. The AE rate will be calculated as the total number of AEs divided by the total patient years of exposure to study drug per treatment group in the parent study.

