11.3 HOSPITALIZATIONS DUE TO CARDIOPULMONARY INDICATIONS

All hospitalizations will be listed including admission date, discharge date, and hospitalization status at the end of the study. Those hospitalizations due to cardiopulmonary indications will be flagged. This listing will be organized by parent study treatment group.

The number and percentage of subjects who experience any hospitalizations and any hospitalizations due to cardiopulmonary indications will be summarized by parent study treatment group and overall. Additionally, the total number of hospitalizations due to cardiopulmonary indications per subject will be categorized by parent study treatment group and overall.

Kaplan-Meier analyses and Cox regression as described in Section 11.2 will also be done.

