11.4 EXACERBATIONS OF UNDERLYING LUNG DISEASE

All exacerbations of underlying lung disease will be listed including start date, end date, status at the beginning and end of the study, whether the exacerbation was considered serious, and if so, the date the event became serious.

The number and percentage of subjects who experience exacerbations of underlying lung disease will be summarized by parent study treatment group and overall. Additionally, the total number of exacerbations of underlying lung disease per subject will be categorized by parent study treatment group and overall.

Kaplan-Meier analyses and Cox regression as described in Section 11.2 will also be performed.

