12.3 LIST OF FIGURES

Figure Number	Figure Title
14.2.1	Mean Change from Baseline in 6MWD (meter) by Visit
14.3.1	Kaplan-Meier Plot of Time to Death
14.3.2	Kaplan-Meier Plot of Time to Hospitalization
14.3.3	Kaplan-Meier Plot of Time to Hospitalization due to Cardiopulmonary Indications
14.3.4	Kaplan-Meier Plot of Time to Exacerbation of Underlying Lung Disease

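### The hospitalization and exacerbation curves censor event-free deaths without saying so; a labelled cumulative-incidence companion and fixed-week estimates would be a cheap improvement

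*SAP*

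**What the plan says.** - **Status rules (SAP 8.5, Table 8-2).** Hospitalization and exacerbation each have an event row and a no-event row. "Subjects without hospitalization during the study" and "Subjects without exacerbation during the study" are censored at the last assessment. Neither endpoint has a row that mentions death.
- **Methods.** SAP 11.3 states "Kaplan-Meier analyses and Cox regression as described in Section 11.2 will also be done", and SAP 11.4 states "Kaplan-Meier analyses and Cox regression as described in Section 11.2 will also be performed". Section 11.2, to which both refer, plans Kaplan-Meier curves, a table with the number at risk and the median with its 95% confidence interval, and an optional Cox model on parent-study arm.
- **Figures (SAP 12.3).** Figures 14.3.2 to 14.3.4 are all Kaplan-Meier plots, for example "Kaplan-Meier Plot of Time to Exacerbation of Underlying Lung Disease". Neither document plans a cumulative-incidence analysis.
- **Other planned outputs.** Sections 11.3 and 11.4 give crude numbers and percentages and per-subject event counts. Section 11.1 adds exposure-adjusted rates: "The AE rate will be calculated as the total number of AEs divided by the total patient years of exposure to study drug". Death has its own time-to-event analysis.
- **Inferential status.** Protocol 10.3: "No formal hypothesis testing is planned".
- **Survival figures.** The only ones in either document are the "one and two year Kaplan-Meier survival estimates of 97% and 91%, respectively" in Protocol 1.2.3, from an extension study in PAH.

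**The concern.** Hospitalization and exacerbation are named safety endpoints, and death can come before either. The two rows of Table 8-2 are exhaustive, so an event-free death is censored like any other subject without the event. The resulting hazard is interpretable as cause-specific. The height of 1-KM is not the proportion of subjects who will have the event, because it describes a setting in which nobody dies first. Readers of a long-term safety report commonly take such curves, and the median read from them, as event probabilities. The crude percentages and the rates are unaffected by this, but neither gives a probability by a stated week.

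A second, smaller gap concerns the table specified in Section 11.2. The median is its only time-to-event estimate. If mortality is moderate, the median time to death is not reached and the table then holds no survival estimate.

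No test, error rate or power is at stake. The issue is how descriptive outputs will be read.

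**Working it through.** The plan states no event rate, death rate or dropout rate for PH-ILD, so there is no planned figure to reproduce. The sizes below are scenarios.

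**Inputs.** From the documents: N = 266 (SAP 6); follow-up of 108 weeks, t = 108×7/365.25 = 2.070 years; survival 97%/91% (PAH). Assumed: one-year event risk r of 15, 30 or 50%, and 80% two-year survival as an alternative.

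**1. Gap with independent discontinuation.** Event hazard h = -ln(1-r); hazard of death without the event d = -ln(S2)/2, where S2 is two-year survival.
- 1-KM = 1 - exp(-ht)
- Cumulative incidence = h/(h+d) × [1 - exp(-(h+d)t)]
- Piecewise version: d = -ln 0.97 = 0.0305 in year 1 and -ln(0.91/0.97) = 0.0639 afterwards.

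| Week 108, % | r = 15% | r = 30% | r = 50% |
|---|---|---|---|
| 1-KM | 28.6 | 52.2 | 76.2 |
| Cumulative incidence, 97%/91% piecewise | 27.5 | 50.4 | 74.0 |
| Gap | 1.1 | 1.8 | 2.2 |
| Gap, 91%, constant hazard | 1.3 | 2.2 | 2.8 |
| Gap, 80%, constant hazard | 2.9 | 4.9 | 6.3 |

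Worked cell (80%, 30%): h = 0.357, d = 0.112; 1-KM 52.2%, cumulative incidence 47.3%. The gap at Week 48 is 1.3 points.

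**2. Against sampling error.** sqrt(p(1-p)/266) at p = 27.3, 50.0 and 73.4% (the 91% constant-hazard case) is 2.7, 3.1 and 2.7 points. The gaps at 91% are at or below this.

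**3. Effect on the median.** At r = 30% the Kaplan-Meier median is ln 2/0.357 = 1.94 years, about 101 weeks. With 80% two-year survival, fewer than half of subjects (47.3%) would have had the event by Week 108.

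**4. Higher mortality after an event.** Step 1 gives death without the event the all-cause rate. If mortality is three times higher after an event and S2 is held fixed, the 91% gaps fall from 1.3/2.2/2.8 to 1.0/1.4/1.5 points. The 80%, 30% gap falls from 4.9 to 3.3, and to 2.5 at a ratio of five.

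**5. Informative discontinuation.** Shared gamma frailty with variance v, discontinuation c per year, H = h+d+c, r = 30%:
- Truth = h/(h+d) × [1 - (1+v(h+d)t)^(-1/v)]
- 1-KM = 1 - (1+vHt)^(-h/(vH))
- Aalen-Johansen = h/(h+d) × [1 - (1+vHt)^(-(h+d)/(vH))]

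Error at Week 108 in points, 1-KM / Aalen-Johansen:

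| S2, c | v = 0.1 | v = 0.25 | v = 0.5 | v = 1 |
|---|---|---|---|---|
| 80%, 0.20 | +3.9 / -0.5 | +2.8 / -1.2 | +1.3 / -1.9 | -0.4 / -2.8 |
| 80%, 0.35 | +3.5 / -0.9 | +1.8 / -2.0 | -0.2 / -3.2 | -2.4 / -4.5 |
| 91%, 0.20 | +1.4 / -0.6 | +0.4 / -1.3 | -0.7 / -2.2 | -2.2 / -3.2 |
| 91%, 0.35 | +0.9 / -1.0 | -0.6 / -2.3 | -2.3 / -3.7 | -4.3 / -5.3 |

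**6. Median time to death.** Reaching it by Week 108 needs a hazard of at least ln 2/2.070 = 0.335 per year, that is, two-year survival of exp(-2×0.335) = 51% or lower.

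**The case against.** The strongest reply has three parts.

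*The rule is stated.* Table 8-2 gives an exhaustive pair of rows with formulas and status codes, the display is legitimate, the Cox hazard ratio is valid as cause-specific, no test is planned, and crude percentages, counts, rates and a death analysis are all there. This stands. It limits the point to labelling and to one added output.

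*The gap is small and stated at its upper end.* This also stands. At the only survival figures in the documents it is within sampling error, and step 4 shows that it shrinks if events raise mortality.

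*The remedy can be further from the truth.* In step 5, 1-KM is the closer curve in 12 of 16 cells: 7 of 8 at 91% survival and 5 of 8 at 80%. The count is right, but it reflects two errors that offset. Censoring deaths pushes 1-KM up and informative discontinuation pulls it down, whereas Aalen-Johansen carries only the second. How far they cancel depends on a dependence that cannot be known in advance. This is a reason to show both curves and not to replace one with the other. It is not a reason to leave the Kaplan-Meier curve unlabelled.

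A reader might also infer that Table 8-2 contradicts Section 11.2, because one censors premature discontinuers while the other counts their deaths within 30 days of the last dose. The documents do not support this. Table 8-2 leaves its event row for death undefined, and on the natural reading that row includes those deaths. Protocol 9.3 already removes events that occur on commercial product.

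**Conclusion.** The point holds as an optional improvement. Event-free deaths are censored without being named, and no planned output estimates the probability of hospitalization or exacerbation by a given week with death taken into account. If discontinuation is independent, 1-KM overstates that probability at Week 108 by about 1 to 3 points at the PAH survival figures, and by about 5 points at an assumed 80% two-year survival and 30% one-year risk. These sizes rest on assumed event risks and on death without the event occurring at the all-cause rate. If mortality is higher after an event they are smaller, and if discontinuation is strongly informative even the direction can change.

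The median-only table is a separate gap. Under a constant hazard it yields an estimate for death only if two-year survival is about 51% or lower.

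Three stronger readings go too far. The Kaplan-Meier and Cox analyses are not invalid. A double-digit overstatement is not supported: the same formula gives up to 16 points, but only at assumed death rates of 20-30% per year, which appear nowhere in the documents. Nor is a new definition of death needed. Extending the 30-day rule to all subjects would go beyond Section 11.2, and censoring all survivors at last dose plus 30 days would leave later on-study deaths off drug as events without matching follow-up.

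**What to change.** 1. In SAP 11.3 and 11.4, keep Kaplan-Meier and add Aalen-Johansen cumulative incidence with death before the event as a competing event. Label the Kaplan-Meier curves *deaths censored* and the Cox hazard ratio *cause-specific*. State that neither curve corrects for informative discontinuation.
2. In SAP 11.2 to 11.4, report Week 48 and Week 108 estimates with 95% confidence intervals beside the median.
3. As wording only: state that the death event row in Table 8-2 uses the same deaths as the Section 11.2 summary. Since SAP 5 plans data cuts and the time-to-death rows do not cover ongoing subjects, state also that these are censored at their last assessment on or before the cut-off.

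The cost is a few sentences, standard software and minor extra programming. Disposition, cut-off and death dates are already in planned listings (SAP 9.1 and 11.2). The downside is that under strongly informative discontinuation the added curve can lie further from the truth than 1-KM, so both should be shown and labelled.

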#### 3.3.2.10 Telephone/Email Contact

Weekly telephone/email contact is required for the first 12 weeks of the study to instruct the subject to titrate their dose of study drug and to assess for AEs and concomitant medications. After the first 12 weeks, telephone/email contact must occur at least monthly.

Telephone/email contact may be replaced by a face-to-face interaction on the weeks where study visits occur and the information can be obtained during the visit. The subject may be contacted via email in lieu of a telephone call; however, email should not replace direct follow-up by telephone or in clinic for clinically significant AEs or other emergent issues. All telephone or email contacts (*i.e.*, any dosing instructions, AEs reported and/or medication changes) with the subject must be noted in the source documentation.

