5 SEQUENCE OF PLANNED ANALYSES

Along with the safety information from the parent study, safety information from the RIN-PH-202 study will be provided to the Data Monitoring Committee (DMC) periodically for safety review.

After study completion and unblinding for the parent study, a data cut for the RIN-PH-202 study will be performed to facilitate the analyses for the RIN-PH-201 study. Analyses based on additional data cuts and the final analyses at the time of study closing will be performed separately.

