8 GENERAL CONSIDERATIONS FOR DATA ANALYSES

All data included in each data cut will be listed. In general, listings will be sorted by subject number and scheduled assessment (if applicable) or the visit date and will be organized by treatment group in the parent study. Listings will include assessment date, assessment time (if available), and study day. Study day is calculated as the assessment date minus the date of the first inhaled treprostinil dose in the RIN-PH-202 study + 1. For data collected on a fixed schedule, the assessment identifier will also be included in the listing.

In general, data will be summarized by visit window. The visit window is calculated based on the time from the first dosing date of inhaled treprostinil in the RIN-PH-202 study. For all presentations of the summary tables, the data will be presented by subjects in the inhaled treprostinil and placebo groups from the parent study (RIN-PH-201) and overall.

For continuous variables, summary statistics will include the mean, standard deviation, median, minimum, and maximum. Minimums and maximums will be expressed using the level of precision to which the variable was collected. All other statistics will be rounded using an additional decimal point. For discrete variables, summaries will include the frequency and percent in each category. Percentages will be rounded to 1 decimal point. Whenever practical, categories of discrete variables will be ordered and labeled as they appear in the Electronic Case Report Form (eCRF), and all categories represented on the eCRF will be included in summaries, even when they do not apply to any subjects in the study.

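### Table 8-2 censors event-free subjects at an undefined last assessment date, which pulls interim Kaplan-Meier event-free curves down; its death rows and its time origin also need repair

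*SAP*

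**What the plan says.** Table 8-2 in SAP section 8.5 defines three times. A subject in the row "Subjects with hospitalization during the study" gets "Hospitalization date – first visit date +1", divided by 7. A subject without the event gets "Last assessment date – first visit date +1", divided by 7, and is censored. Exacerbation follows the same pattern. For death, the only censoring row is "Subjects who completed or discontinued prematurely". The SAP defines neither the first visit nor the last assessment, and Table 8-2 names no cut-off date.

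Elsewhere the SAP counts from the first open-label dose: "Study day is calculated as the assessment date minus the date of the first inhaled treprostinil dose in the RIN-PH-202 study + 1" (section 8). Section 8.4 uses that same dose for Baseline and the visit windows.

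Section 5 plans a cut after the parent study is unblinded and then says "Analyses based on additional data cuts and the final analyses at the time of study closing will be performed separately". Section 8 adds "All data included in each data cut will be listed". The times feed the Kaplan-Meier summaries and possible Cox models of sections 11.2 to 11.4 and the four Kaplan-Meier figures listed in section 12.3.

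Visits fall at Weeks 4 and 12 and then 12 weeks apart (Protocol 3.1). Between visits there are weekly contacts up to Week 12, and "After the first 12 weeks, telephone/email contact must occur at least monthly" (Protocol 3.3.2.10).

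**The concern.** Hospitalizations and exacerbations are recorded continuously from consent (Protocol 3.3.2.8 and 3.3.2.9), and serious events are reported within 24 hours of awareness (Protocol 9.4). An event between the last visit and the cut can therefore be in the data. A subject with such an event keeps the time up to it. A subject without one loses all time since the last assessment, which can approach 12 weeks. Events stay in while event-free time is removed, so the Kaplan-Meier risk sets are too small. Long-term safety is a secondary objective, and these curves are one of its main displays at each cut.

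Two further defects sit in the same table. A subject alive and in the study at a cut fits no death row, so the table gives that subject no survival time. And Baseline data come from the parent study's Week 16 visit, before open-label dosing (Protocol 7.1), so the first visit may precede SAP Day 1.

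**Working it through.** The plan gives no event rate, sample size calculation or power figure to reproduce. The check compares Table 8-2 with follow-up that ends at the cut for everyone.

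**Inputs from the documents.** Clinic visits at Weeks 0, 4, 12 and then every 12 weeks; contacts weekly to Week 12 and then monthly, taken here as every 4 weeks.

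**Assumptions not in the documents.** Follow-up at the cut is uniform from 0 to M weeks, with M = 26, 52 or 104. Event times are exponential at 0.1 to 0.2 per year. There is no dropout, and events are known up to the cut. For death, ongoing subjects are treated like the other event-free subjects, because the table has no row for them.

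**1. Censoring, low-hazard approximation.** Let d be the successive intervals between assessments that cover 0 to M. The mean time lost is L = Σd²/(2M), and the rate ratio is (M/2)/(M/2 − L).

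| M | Last assessment | Σd² | L (weeks) | Ratio | Simulated, hazard 0.1 to 0.2 |
|---|---|---|---|---|---|
| 26 | visit | 16+64+144+4 = 228 | 228/52 = 4.38 | 13/8.62 = 1.51 | 1.49 to 1.50 |
| 52 | visit | 16+64+3×144+16 = 528 | 528/104 = 5.08 | 26/20.92 = 1.24 | 1.23 to 1.24 |
| 104 | visit | 16+64+7×144+64 = 1152 | 1152/208 = 5.54 | 52/46.46 = 1.12 | 1.11 |
| 26 | contact | 12×1+3×16+4 = 64 | 64/52 = 1.23 | 13/11.77 = 1.10 | 1.10 |
| 52 | contact | 12×1+10×16 = 172 | 172/104 = 1.65 | 26/24.35 = 1.07 | 1.06 to 1.07 |
| 104 | contact | 12×1+23×16 = 380 | 380/208 = 1.83 | 52/50.17 = 1.04 | 1.03 to 1.04 |

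The ratio hardly depends on the hazard. It depends on how long follow-up is and on what counts as an assessment.

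**2. Effect on the curve** (hazard 0.2, M = 52, visits only). Kaplan-Meier survival is too low by 0.3, 1.2 and 2.6 points at Weeks 12, 24 and 36. At Week 47 it reads 76% against a true exp(−0.2×47/52.18) = 83.5%, but only about 6% of subjects are still at risk there. With contacts counted it reads 82%.

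**3. Final analysis.** If every subject is followed to Week 108 and assessed there, last assessment and end of follow-up coincide and the ratio is 1.00.

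**4. Origin.** A first visit g weeks before the first dose adds time in which no death can occur, because the Safety Population requires a dose (SAP section 7). The ratio is about (M/2)/(M/2 + g). For g = 1 week it is 13/14 = 0.93, 26/27 = 0.96 and 52/53 = 0.98 at M = 26, 52 and 104. If visit and dose fall on the same day there is no effect.

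**5. Both together** (M = 104, annual risk 20%). Gaps of 7 and 28 days give net ratios of 1.08 and 1.01 with visits, and 1.01 and 0.95 with contacts.

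**The case against.** The case for treating this as wording only has real content.

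- **Contacts can be read as assessments.** Subjects are questioned about adverse events at telephone and email contacts (Protocol 3.3.2.6). Under that reading the inflation is 3% to 10%. This stands as a reading, but the SAP does not adopt it.
- **No document gives a 26-week cut.** The 50% figure is the upper end of an assumed range. That stands.
- **That events run to the cut is an inference.** Table 8-2 speaks only of events during the study. If events became known only at assessments, the bias would largely vanish. Continuous recording and 24-hour serious event reporting make that unlikely for deaths and hospitalizations.
- **Censoring everyone at the cut has its own bias.** If events surface only at contacts, the rate is understated by about 1 − 1/1.04 = 4% to 1 − 1/1.10 = 9%. This stands, and it is why the fix requires confirmed status.
- **The reach is limited.** Adverse event rates use exposure years (SAP section 11.1), counts and percentages do not use these times, the Cox model for death is optional, and no formal testing is planned (Protocol 10.3).

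A reader might also infer that the first-visit origin adds to the upward bias. It does not: extra time that cannot contain a death lowers the rate. Hospitalizations or exacerbations between consent and first dose, if counted, could act the other way. A reader might further infer that the final safety report is mis-stated. The documents do not support that, because subjects who leave early are to have a Study Termination Visit (Protocol 7.3).

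**Conclusion.** The point holds for interim cuts. Applied as written, Table 8-2 makes follow-up depend on outcome for subjects still in the study and biases the Kaplan-Meier event-free curves downward. Under the stated assumptions the person-time rate is inflated by about 11% to 50% if assessments are clinic visits and 3% to 10% if contacts count. In the 52-week example, survival is off by 1 to 3 points at Weeks 24 to 36 and by more only in the thin tail. A Cox model would use the same times; the shift in its hazard ratio was not computed and need not be the same size, since both parent groups are affected.

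The final analysis is largely unaffected, apart from subjects lost to follow-up and any deaths counted up to 30 days after the last dose (SAP section 11.2). The missing death row and the inconsistent origin are separate defects. The origin acts downward if the first visit comes first, and an offset from a gap of unknown length is no safeguard. It is worth correcting before any cut is analysed.

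**What to change.** Amend Table 8-2 as follows:

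- Use the first RIN-PH-202 dose date as origin for all three variables.
- Add a row for subjects ongoing at a data cut, including those alive for the death analysis.
- Censor event-free subjects at the cut-off date when their status is confirmed to that date. Otherwise censor at the last date known event-free, by visit or documented contact (for death, last known alive).
- For subjects who left, state the risk period and censor at its end or at the last date known event-free, whichever is earlier.
- Count only events inside that same period.

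The cost is SAP wording, reprogramming of three derived variables, and a status check at each cut. The cut-off date is already in the disposition listing (SAP section 9.1). Contact records are held in source documents and not expressly in the eCRF, so using those dates may need some extra data capture.
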